Study Visit 1 (primary care office): Once consented and randomized, the CHW will collect baseline data (study questionnaires, weight, height, spirometry), administer a caregiver needs assessment and assist caregiver in choosing 2-3 care coordination goals such as keeping appointments, reduce secondhand smoke exposure or using medications correctly. The CHW will conduct in-office asthma teaching (medications/devices/asthma care plan), coordinate specialist visits and assist caregivers in voicing questions/concerns about medications or treatment plans to the primary care provider. They will personally schedule patients for follow-up visits with the primary care provider. Home Visits 1, 2 and 3: The first three home visits will occur within 2, 4 and 6 weeks after enrollment. At the first visit the CHW will conduct an environmental assessment of the living area and bedroom for common asthma triggers. Based on those findings the CHW will educate regarding asthma trigger avoidance and give supplies to reduce those triggers (mattress and pillow covers, roach bait, mice traps, tiles for carpeted floors) at the second visit. The CHW will also review medications available for the child at home and whether forms/prescriptions have been completed for school. They will coordinate with the primary care team as needed. Video conferencing through a HIPAA-compliant application licensed by CHOP, including but not limited to Vidyo telehealth visits in MyCHOP, may be used for home visits that cannot be conducted in person due to health or safety concerns. For telehealth home visits, supplies will be provided to families via U.S. postal mail with caregivers providing confirmation of receipt. Study Visits 2, 3, and 4 (primary care) will occur at 3, 6, and 9 months post-randomization. At these visits, the participants will receive asthma maintenance care by the provider/clinician and pulmonary function testing (spirometry) in addition to the education and care coordination activities by the CHW as described in the first visit. A member of the research team other than the assigned CHW (Home Visitor) will administer study questionnaires at these visits. At Home Visit 4 at 12 months post-randomization the CHW will conduct an environmental assessment to document trigger reduction techniques in the home and review medications. At Study Visit 5 at 12 months post-randomization, the asthma control questionnaire (ACQ), additional study questionnaires, pulmonary function testing (spirometry) and care coordination goals will be completed. Study staff will administer a CHW satisfaction survey via telephone between 13 and 24 months post-randomization once all primary care and school interventions have been completed.

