Asthma control is the primary outcome of this study. Symptom-free days, and school absences are secondary outcomes in this study. Asthma control has been cited by the NAEPP guidelines and asthma outcomes workshop as an important goal for prevention of asthma morbidity. In several studies, poor asthma control, whether defined by the patient (using self-reported, validated instruments) or by national asthma guideline classifications, has been strongly associated with an increased risk of asthma exacerbations which may lead to emergency room visits, hospitalizations and even death. Asthma control will be measured using Juniper's Asthma Control Questionnaire, a validated instrument for children and adults. Symptom-free days will be based on parental report recall of the last two weeks, consistent with previous studies. School absences will be measured by school and parental report. Additional secondary outcomes will include asthma-related emergency

visits and hospital visits (obtained from CHOP EHR), and cost-savings. Moderator variables will be measured using the CARAT survey which is a Child Asthma Risk Assessment Tool designed to help clinicians, asthma counselors and parents determine potential risks for children with asthma.

Data will be collected for all individually randomized participants at baseline, 3, 6, 9 and 12 months by a member of the research team in person or by phone. Participants will be compensated \$25 for each visit with data collection at baseline, 3, 6, and 9 months and \$45 for the end of study visit at 12 months.

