### 5 STUDY EVALUATIONS AND MEASUREMENTS

### 5.1 Individual Participant Measures

- Children will be measured for **height and weight** (using standard scales and stadiometers), **blood pressure**, **pulse**, **temperature**, and **pulse oximetry** (SpO2) at baseline, 3, 6, 9, and 12 months following enrollment. This information may also be abstracted from the medical record.
- Pulmonary function tests (spirometry) will be abstracted from the electronic health record if possible. If spirometry is not completed by the child's healthcare team as a part of usual clinical care, it will be completed by a trained community health worker at baseline, 3, 6, 9 and 12 months post-enrollment. Each recording will be printed out to become a part of the child's medical record. Pulmonary function testing completed for clinical purposes within one month before or after a baseline or

- follow-up study visit will be abstracted from the medical record if testing is unable to be completed at the time of a study visit.
- Juniper's **Asthma Control Questionnaire** is a validated survey and will be administered by a member of the research team to the parent/caregiver by reading out loud to avoid any literacy barriers. This will be administered at baseline, 3 months, 6 months, 9 months and 12 months
- A home **environmental assessment** will be conducted by a CHW in the living room and child sleeping area to note common triggers such as dust, pests, pets, mold and tobacco smoke measured at Home Visits 1, 2, 3, and 4.
- CAPP's **asthma knowledge survey** will be used to assess knowledge at home visits before, during and after the primary care intervention. This survey may be administered out loud to the parent/caregiver to avoid any literacy barriers.
- CHW will ask parent/caregiver for a 2-week recall of daytime cough or wheeze, nighttime cough or wheeze, missed school days, missed parent workdays at the time of the visit. This will be recorded on a tracking form in REDCap.
- The Caregiver Needs Assessment will be administered to the parent/caregiver at the baseline visit. The needs assessment is a validated instrument that focuses on the caregiver's knowledge about asthma avoidance measures and their comfort level with managing their child's asthma. For participants receiving the primary care intervention, this tool will assist the primary care community health worker with tailoring the educational component of the program to fit the needs of the individual family.

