### 6.3.2 Efficacy Analysis

The primary analysis will be based on an intention to treat approach and will include all subjects randomized at Study Visit 1. The primary efficacy endpoint will be the change in asthma control between Study Visit 1 and Study Visit 5. Secondary efficacy endpoints will include the change in asthma symptom days and school absences between Study Visit 1 and Study Visit 5.

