3.4 Allocation Concealment

For the individual child level randomization, all randomization lists were generated by one of the statisticians and then delivered to the REDCap database designers. Upon each child recruitment, REDCap then produced the treatment assignment for the next child and for the school of the child's attendance. All patients had to consent to the study (and sign consent forms) before the research coordinator could elicit from REDCap the treatment assignment for that child. By this method no one on the staff other than the database manager was aware of the next treatment assignment for the next child in the stratum of school*clinic.

4 Data Collection and Management

Data will be collected, accessed, and stored by the CHWs and study research team. Any paper forms will be stored in locked cabinets in the Community Asthma Prevention Program's (CAPP) badge-only accessible suite. Data collected using REDCap is accessible only by the CHWs and research study staff. Designated school administrators (i.e., principal), the school nurse and the child's primary care provider will only have access to participant health care information necessary to conduct asthma management in the schools and primary care office, but none of the research data collected by the CHWs and study staff. Information will be kept confidential under HIPPA guidelines and Institutional policies. Analysis will proceed on CHOP computers, either secure desktop machines or the CHOP virtual computing system based on VMWare, and all data will be stored on a CHOP server in directories created for this project. Access to each dataset with identifiers will be limited to the minimum necessary to accomplish the analytic tasks.

5 Analysis – Primary

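### The rule that keeps the assigned CHW from administering questionnaires covers Visits 2–4 but neither visit that defines the primary endpoint, and P+ baseline questionnaires follow randomisation, so P contrasts carry an avoidable risk of measurement bias

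*Protocol*

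**What the plan says.** **Baseline, P+.** In Protocol 3.1.2, Visit 1 reads: "Once consented and randomized, the CHW will collect baseline data (study questionnaires, weight, height, spirometry". The same CHW sets goals and teaches at that visit.

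**Release of the assignment.** Under SAP 3.4 all patients "had to consent to the study (and sign consent forms) before the research coordinator could elicit from REDCap the treatment assignment". No completed baseline is required.

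**Assessor rule.** After placing Visits 2, 3 and 4 at 3, 6 and 9 months, Protocol 3.1.2 says: "A member of the research team other than the assigned CHW (Home Visitor) will administer study questionnaires at these visits". Its sentence on Visit 5 names no assessor.

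**Endpoint.** Protocol 6.3.2: "The primary efficacy endpoint will be the change in asthma control between Study Visit 1 and Study Visit 5". The analysis "will include all subjects randomized at Study Visit 1".

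**Who asks, elsewhere.**
- Protocol 3.1.3 has data collected "at baseline, 3, 6, 9 and 12 months by a member of the research team in person or by phone".
- Protocol 5.1 says the ACQ "will be administered by a member of the research team to the parent/caregiver by reading out loud".
- Protocol 5.1 on the symptom recall: "CHW will ask parent/caregiver for a 2-week recall of daytime cough or wheeze, nighttime cough or wheeze". It gives no visit limit and does not exclude the assigned CHW. Table 1 makes this recall part of the follow-up questionnaire.
- Protocol 9.7.1 allows a research assistant or the primary care CHW at all five time points.
- SAP 5.1.2 (Measuring outcomes over time) gives the ACQ to the CHW at all five time points.

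**Blinding.** Protocol 9.1.2 mentions only the principal investigator.

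**P- baseline.** Protocol 4.2.1 lists the Visit 1 items for all participants but does not say where randomisation falls among them.

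**The concern.** The ACQ is a caregiver report, spoken to a member of staff. If the person asking, or knowledge of the allocation, differs between P+ and P- at Visit 1 or Visit 5, the difference enters the change score and randomisation does not remove it. The plan already keeps the assigned CHW away from the questionnaires at the three intermediate visits, but the endpoint is formed from the other two.

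The direction is not predictable. A shift toward better control at baseline alone works against P+; the same shift at Visit 5 alone favours it; an equal shift at both cancels.

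The exposed contrasts are those that differ in P: P+ v P- (A+ v A- in the SAP), and cells a vs b, a vs d, b vs c and c vs d. They include one of the two main effects in Aim 1a. S+ v S-, a vs c and b vs d compare like with like on P and are largely protected, provided the shift does not depend on the school arm. Symptom days share the problem through the recall. ED and hospital counts come from the health record and do not.

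**Working it through.** **Coverage of the rule**

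| Visit | Assigned CHW excluded (Protocol 3.1.2) | Forms the primary endpoint (Protocol 6.3.2) |
|---|---|---|
| 1 (baseline) | No; the CHW collects | Yes |
| 2, 3, 4 | Yes | No |
| 5 (12 months) | Not stated | Yes |

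**Inputs for the illustration**
- n=432, so 216 per P arm, and a P effect of 0.35 SD of change (SAP section 8).
- Significance level 0.05, taken as two-sided; the documents do not state sidedness.
- 0.5 SD equals 0.4 ACQ points (Protocol 6.4), so 1 SD = 0.4/0.5 = 0.8 points.
- Net shift b of 0.05–0.15 SD at one end visit. This is my assumption; the documents give no value. It equals 0.04–0.12 points, and 0.05/0.35 = 14% to 0.15/0.35 = 43% of the planning effect.

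**Plan's own figure.** SE = 2/√432 = 0.0962. Power = Φ(0.35/0.0962 − 1.96) = Φ(1.677) = 0.953. SAP section 8 gives 0.95, so the simple formula reproduces it.

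**How much of the shift passes into the estimate (k).** With visits at 0, 3, 6, 9 and 12 months:
- Two-visit change, or a spline with five time parameters (linear with knots at 3, 6, 9, or restricted cubic with knots at 0, 3, 6, 9, 12): the weights are −1, 0, 0, 0, 1, so k = 1.
- Straight line in time: the weights are 12(t − 6)/90 = −0.8, −0.4, 0, 0.4, 0.8, so k = 0.8. With a random intercept only, the SE ratio is √(1.6/2) = 0.894; with no gain in precision it is 1.
- Late visits, which SAP 5.1.2 expects: with linear splines and an assumed mean lag of about 0.8 month, a Visit 5 shift passes at about 0.7. A Visit 1 shift still passes in full.

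**False-positive rate with no true P effect** = Φ(−1.96 − kb/SE) + 1 − Φ(1.96 − kb/SE):

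| Case | kb/SE at b = 0.05, 0.15 | Rate |
|---|---|---|
| k = 1 | 0.520, 1.559 | 8% to 34% |
| k = 0.8, SE ratio 0.894 | 0.465, 1.394 | 7.5% to 28.6% |
| k = 0.8, SE ratio 1 | 0.416, 1.247 | 7.0% to 23.9% |
| k = 0.7, SE ratio 1 (late Visit 5) | 0.364, 1.091 | 6.5% to 19.4% |
| k = 1, half of P+ scores affected (b halved) | 0.260, 0.779 | 5.8% to 12.2% |
| Equal shift at both visits | 0, 0 | 5% |

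**If the shift runs against P+**, a true 0.35 SD becomes 0.30 or 0.20 SD at k = 1, and power falls from 0.953 to 0.877 or 0.547.

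**Cost of dropping baseline.** The SE of a 12-month comparison relative to the change score is 1/√(2(1 − ρ)): 0.85, 1.0 and 1.29 for ρ = 0.3, 0.5 and 0.7. These correlations are assumed.

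**The case against.** **Visit 5 is silent, not assigned to the CHW.** This stands. A reader might infer that the assigned CHW is instructed to take the 12-month ACQ in P+. Protocol 3.1.2 does not say so. Protocol 9.7.1 only permits it, and the SAP names the CHW in a remark about irregular visit times. Protocol 9.2 lists CHWs and the research team separately, which supports reading the research-team wording in 3.1.3 and 5.1 as excluding CHWs. The assessor rule in 3.1.2 points the other way, since it has to exclude the assigned CHW by name. The text is ambiguous, and no section closes the gap.

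**Section 4 treats assessment as common to both arms.** Protocol 4.2 lists the questionnaires for all participants, and 4.3.1 adds only P+ coordination tasks. That is fair, but Section 4 names no assessor. A reader might also infer that P- baselines precede randomisation while P+ baselines follow it. The documents do not show that: SAP 3.4 has one consent condition for both arms, and the P- order is simply unstated.

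**A uniform reading removes the difference.** If one class of staff assesses everyone at every visit, a constant shift cancels, and no section prescribes a change of assessor that differs by P arm. This weakens the case without ending it. Even if a CHW asks everyone, by Visit 5 only P+ caregivers could be answering someone who has spent a year helping them.

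**The shift size is a guess, and caregivers know their arm whoever asks.** Both stand. The percentages only illustrate sensitivity, and a common assessor reduces the risk without removing it.

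**Conclusion.** The gap in the rules is real and should be fixed; a bias is not demonstrated. The stated procedures put P+ baseline questionnaires after randomisation in the hands of the person delivering the intervention, protect only Visits 2–4, and conflict on the assessor elsewhere. The P contrasts on the Visit 1 to Visit 5 change are therefore open to a shift whose presence, direction and size are unknown.

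The 8–34% range needs three things together: a net shift of 0.05–0.15 SD, at one end visit only, passing in full. For a late Visit 5 the effect is smaller, and with equal shifts at both visits it is nil. Planned sample size and power are not in question. Confidence is medium, because actual practice may have been more uniform than the text.

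**What to change.** 1. For any child still to be enrolled, require the baseline ACQ and two-week recall to be completed in REDCap before the assignment is released, in both P arms. Spirometry need not be a condition, because Protocol 5.1 accepts clinical results from within a month either side of the visit.
2. For any Visit 5 still to occur, apply the existing rule that excludes the assigned CHW, and use the same type of existing research staff in both P arms.
3. Reconcile Protocol 3.1.2, 3.1.3, 5.1 (ACQ and recall) and 9.7.1 and SAP 5.1.2 to that rule, and state the baseline order for P-.
4. For data already collected:
   - If recorded, report by P arm who administered the Visit 1 and Visit 5 ACQ, and whether baseline preceded allocation. The documents do not say that either was recorded.
   - Add a sensitivity analysis of the P contrasts on the 12-month ACQ without baseline. This removes any baseline-order effect but does not address the Visit 5 assessor. Both arms have a 12-month office visit.
   - Where the assessor was recorded, shift CHW-taken Visit 5 scores until the conclusion changes and report that point. Do not cap the shift at the 0.12 points used in the illustration.

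The cost is wording in both documents, one REDCap check, some scheduling of staff already used at Visits 2–4, and up to two extra analyses. The 12-month analysis has 0.85 to 1.29 times the SE of the change score under the assumed correlations.

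SAP 3.2 describes child randomisation in the past tense. If enrolment and follow-up are closed, items 1 and 2 come too late and only items 3 and 4 apply. Baselines already taken cannot be re-ordered, and caregivers remain unblinded in any case.

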
#### 3.1.3 School Based Intervention

West Philadelphia elementary schools who have agreed to participate will be randomized to either receive the school intervention facilitated by a school CHW or usual school care (no intervention). Intervention schools will receive Open Airways for Schools *Plus* designed by Clark, et. al. to improve the disease management skills of children with asthma and enhance control of asthma in the school. It contains four "essential components" of the recently published School-based Asthma Management Program (SAMPRO) summit guidelines and has been found to decrease both asthma symptom days and school absences. The school intervention includes: (1) **Open Airways for Schools**® curriculum for all children with asthma. One class series will be conducted by the school CHW each semester. (2) Orientation to asthma and control strategies for principals and school personnel at the start of each school year led by the study team along with the school CHW, (3) For School District of Philadelphia public schools, walk-throughs for custodial personnel to address potential environmental asthma triggers. This will be managed and conducted by school district personnel, and (4) Assistance with obtaining asthma care plans and medication administration forms from primary care provider offices facilitated by the school CHW.

For participants assigned to both interventions, the school and primary care CHWs will collaborate to coordinate care across the school nurse and primary care offices. In addition to the primary care and school interventions above, this treatment group will receive enhanced coordination with **School-Based Asthma Therapy** for prescribed daily controller medication. The primary care CHW will obtain a copy of the current asthma care plan, school medication administration form, a rescue inhaler prescription for school, and an asthma controller medication prescription to conduct school based asthma therapy. Prescriptions for rescue inhalers and asthma controller medications will be dispensed before the child leaves the primary care office. Depending on the participant's health insurance coverage the prescriptions may be filled using an automated medication dispensing system (mobile pharmacy) at Cobbs Creek, Karabots, and South Philadelphia CHOP primary care practices or through an internal pharmacy at a Federally Qualified Health Center. Primary care CHWs will deliver current asthma care plans, medication administration forms, rescue

inhalers (if applicable), and asthma controller medications (if applicable) directly to School CHWs at weekly team meetings. School CHWs will deliver these items to the school nurse to file/store in a designated location in the school nurse's office. The school nurse and/or School CHW will coordinate with teachers to schedule an intake appointment for children receiving school based asthma therapy at which the nurse will complete a metered dose inhaler (MDI) checklist with the child to assess ability to self-administer medications and to schedule a time for the child to return to the office for daily medication administration. Medication use (both rescue and controller) will be recorded by the school nurse or school CHW. If nurse is not present, as per usual school protocol, the principal will be responsible for assigning this task. For this treatment group, asthma management skills will be reinforced at home, school and in the primary care office.

Families of children who are not randomized to the primary care intervention will be offered Community Asthma Prevention Program (CAPP) asthma classes, conducted at community sites, which are available to the general public. Data will be collected from the control arm at 3, 6, 9 months by phone or in person. At 12 months an office visit will be scheduled, pulmonary function testing (spirometry) performed and end-of-study data collected. After completing the study these patients will receive one home visit from a primary care CHW to complete an asthma trigger assessment and distribute asthma trigger reduction supplies.

Schools who are not randomized to intervention arm will be offered training after the study data collection period has ended and during the last year of grant funding in how to implement the school asthma interventions and will be provided with information on how to sustain these interventions by obtaining reimbursement from health insurance companies for school CHW services.

During the COVID-19 pandemic, the study activities detailed above will be modified as follows to preserve the health and safety of participants, healthcare professionals, study staff and the West Philadelphia community. Data collection for study visits may take place remotely by telephone or video conference using a HIPAA-compliant application licensed by CHOP. In person clinic visits solely for study purposes will take place as permitted by CHOP Research Institute Policy and Guidelines. Study activities designed to take place in a school setting may take place remotely by telephone or video conference using a HIPPA-compliant application licensed by CHOP.

Asthma control is the primary outcome of this study. Symptom-free days, and school absences are secondary outcomes in this study. Asthma control has been cited by the NAEPP guidelines and asthma outcomes workshop as an important goal for prevention of asthma morbidity. In several studies, poor asthma control, whether defined by the patient (using self-reported, validated instruments) or by national asthma guideline classifications, has been strongly associated with an increased risk of asthma exacerbations which may lead to emergency room visits, hospitalizations and even death. Asthma control will be measured using Juniper's Asthma Control Questionnaire, a validated instrument for children and adults. Symptom-free days will be based on parental report recall of the last two weeks, consistent with previous studies. School absences will be measured by school and parental report. Additional secondary outcomes will include asthma-related emergency

visits and hospital visits (obtained from CHOP EHR), and cost-savings. Moderator variables will be measured using the CARAT survey which is a Child Asthma Risk Assessment Tool designed to help clinicians, asthma counselors and parents determine potential risks for children with asthma.

Data will be collected for all individually randomized participants at baseline, 3, 6, 9 and 12 months by a member of the research team in person or by phone. Participants will be compensated \$25 for each visit with data collection at baseline, 3, 6, and 9 months and \$45 for the end of study visit at 12 months.

